#### 9.6.1.2 Parent version (not included in AYA surveys)

**9.6.1.2.1 Generalized Anxiety Disorder Screener (GAD-7).** This 7-item survey is commonly used to identify cases of generalized anxiety disorder and to assess symptom severity. Participants are asked how often during the last two weeks they have been bothered by each of the 7 core symptoms of generalized anxiety disorder. Response options include “not at all,” “several days,” “more than have the days,” and “nearly every day,” scored as 0, 1, 2, and 3, respectively. Therefore, GAD-7 score range from 0 to 21, with scores of  $\geq 5$ ,  $\geq 10$ , and  $\geq 15$  representing mild, moderate, and severe anxiety symptoms levels, respectively. Internal consistency was acceptable ( $\alpha=0.89$ ). Inter-correlations ranged from  $r = 0.45$  to  $r = 0.65$ . This instrument is included in the full (not abbreviated) surveys for the RCT.

**9.6.1.2.2 Patient Health Questionnaire (PHQ-8).** This 8-item survey is widely used among general populations, patients with chronic illness, and in parents of children with cancer. It is identical to the also widely used PHQ-9, with the exception that PHQ-8 deletes a question about suicidal ideation. Research indicates that the deletion of this question has a minimal effect because self-harm thoughts are relatively rare and this item is the least commonly endorsed item on the 9-item survey. Furthermore, the original validation studies of the two instruments demonstrate similar psychometrics and identical thresholds for depression severity. The instruments have excellent psychometric properties ( $\alpha=0.86-0.89$ ). Each item is scored on a 4-point Likert scale and the sum (0- 27) indicates the degree of depression, with scores of  $\geq 5$ ,  $\geq 10$ , and  $\geq 15$  representing mild, moderate, and severe depression. Scores correlate with functional status and are sensitive to behavioral interventions. This instrument is included in the full (not abbreviated) surveys for the RCT.

**9.6.1.2.3 Medical Outcomes Study Rand 36-item Health Survey (SF-36).** The SF-36 is the most widely used generic measure of HRQOL among U.S. Adults. It incorporates 8 concepts: physical functioning, body pain, limitations due to physical health problems, role limitations due to personal or emotional problems as well as emotional well-being and social functioning, energy, fatigue and general health perceptions. It includes a single item regarding perceived change in health. Internal reliability ranges from  $\alpha=0.78-0.93$ . This instrument is included in both the full and abbreviated surveys for the RCT.

**9.6.1.2.4 Hospital Consumer Assessment of Healthcare Providers and Systems (HCAHPS).**

This survey is a widely used and standardized tool to measure patient and family perspectives on hospital care. It has been endorsed by the National Quality Forum (NQF) in order to allow for cross-hospital comparisons. The survey includes a core set of questions that can also be combined with customized project- or site-specific items. For this study, we have included domains regarding care for teenaged patients, communication and child-centered care, and overall hospital ratings. All items are scored on a Likert Scale (for example, to the question "During this hospital stay, how often did providers involve your child in discussions about his or her health care?" response options include "Never," "Sometimes," "Usually," and "Always." This instrument is included in the full (not abbreviated) surveys for the RCT.

**9.6.1.3 Both AYAs and Parents**

**9.6.1.3.1 The Decision-Making Involvement Scale (DMIS).** The 30-item DMIS was

developed to assess child and adolescent involvement in decisions having to do with illness management. Specifically, items assess child- and parent-behaviors that reflect the way children are involved in decisions, regardless of who ultimately makes the decision. Both AYAs and parents are asked to reflect on an important conversation from the past month and then respond to items based on a 4-point Likert Scale. Although there is a potential total score, instrument authors suggest scoring based on subscales assessing specific dimensions of involvement, including "child seek," "child express," "parent seek," "parent express," and "joint/options." Range of scores for each subscale = 0-4 and Cronbach's alpha = 0.68-0.71. This instrument is included in full and abbreviated surveys for the RCT.

**9.6.1.3.2 The Survey about Caring for Children with Cancer (SCCC).** This

questionnaire was developed from literature and focus groups of parents and medical providers to identify key domains relevant to caring for children with advanced cancer. Items were adapted from existing validated surveys and evidence-based guidelines. The survey has been extensively tested for content, wording, response burden, and cognitive validity. It has been used in multiple pediatric palliative care clinical trials, with several key analyses conducted by the PI. For this study, we included select items to assess parent-/patient- perceptions of prognosis, treatment goals, ability to express hopes and worries, as well as questions assessing satisfaction with overall care, and an ad-hoc checklist querying the number and duration of discussions the family has with health-care, psychosocial, or palliative care teams regarding prognosis, treatment goals, AYA hopes and worries, and to what degree AYAs

were involved in such discussions. This instrument is included in full and abbreviated surveys for the RCT and the run-in.

**9.6.1.3.3 The COVID-19 Impact Questionnaire. (COVID-IQ)** This 7-item, self-report questionnaire was developed for this study to assess perceived impact of the COVID-19 pandemic on AYAs and parents. Items assess worry/anxiety related to COVID-19, life events as a result of COVID-19 (e.g., loss of job, missed school), lifestyle changes (e.g., social distancing), and known COVID-19 symptoms/diagnoses/treatments of self and family members. Respondents are invited to provide free text responses for two additional items: 1) “What is helping you through the COVID-19 pandemic” and 2) “Please tell us about other effects of COVID-19 on yourself, your child(ren) and/or your family, both negative and/or positive.” Lastly, respondents are asked to rate the extent to which their responses to other survey questionnaires were impacted by the COVID-19 pandemic.

## 9.7 Optional Heart Rate Variability Procedures

### 9.7.1 Data Collection

HRV will be measured using the Actiheart 5 external device (CamnTech, Inc, UKFDA class 2, 510(k) number K052489). The Actiheart 5 is an FDA-approved, lightweight, wireless electrocardiogram (ECG) monitor that attaches to a patient's torso via two standard ECG electrodes. Patients who consent to the optional HRV measurement portion of the study will be given their Actiheart monitor at enrollment. A study CRA or investigator will place the monitor on the patient and ensure adequate ECG signal acquisition, or a study CRA will instruct the patient on placing the monitor themselves. The patients will wear the monitor for a 24h period, and then return the device to a study team member. The devices will be collected at the next planned clinic appointment if outpatient, or the next day if inpatient.

The HRV monitoring would not be expected to affect the subject's usual clinical care. Subjects could undergo lab draws, clinic visits, receive chemotherapy, and maintain their usual level of activity without interference from the HRV monitor. If a subject needed to undergo emergent imaging of the chest (where the HRV device may obstruct some of the visual field), or an emergent surgical procedure while wearing the monitor, it would simply be removed. The study team would otherwise coordinate HRV monitor placement so that it does not overlap with planned chest imaging or surgical procedures. If a subject need to remove the monitor for any reason, we would not expect the subject to replace and wear the monitor again during that 24-hour recording period.

### 9.7.2 Data Collection Schedule

HRV data will be collected at clinically relevant and study specific time intervals where possible (**Table 6**). When not possible, HRV data collection will be scheduled at the patient's convenience.

**Table 6. HRV data collection schedule**

Time Point	T1 (Baseline)	T2 (PRISM session #1)	T3 1 month (survey timepoint)	T4 3 months (survey timepoint)	T5 6 months (survey timepoint)
Where?	In clinic/at home OR inpatient	In clinic/at home OR inpatient	In clinic/at home OR inpatient	In clinic/at home OR inpatient	In clinic/at home OR inpatient
How long?	24 hours	24 hours	24 hours	24 hours	24 hours

## 10.0 Data and Specimen Banking

### 10.1 Data Storage and Confidentiality

De-identified data (including medical record, RPCA survey data, and transcripts of recorded sessions and/or interviews) will be stored indefinitely within a database saved on a password protected server at Seattle Children's Research Institute. Upon completion of data collection, SCH will transfer the limited dataset to DFCI per the Data Transfer Agreement. Original surveys will be saved at SCH for 10 years or until final analyses are completed, whichever occurs last, in order to ensure data quality. Only study staff with human subjects training will have access to the data, subject to approval by the SCH site PI, [name]. De-identified study data will be banked indefinitely for future use by the group of investigators conducting the study and access will be controlled by the PI's. PIs will verify that additional analyses have IRB approval. No data will be withdrawn from the study database. Results of initial analyses will be shared with participants if participants request on the consent form that they would like a summary of study results.

### 10.2 Data and/or Sample Sharing

Data will not be shared outside the group of investigators conducting the study but will be fully shared during and after the study with investigators in the group. When other investigators are interested in new analyses, the PIs will verify they have IRB approval to conduct additional analyses. De-identified study data will be banked indefinitely for future use by the group of investigators conducting the study and access will be controlled by the PI's. Future studies will formally test the intervention once its feasibility is confirmed. Should the intervention be effective, it will be made publicly available for use by the broader medical communities caring for AYAs with serious illness.

## 11.0 Data Analysis/Management

**11.1 Run-In Cohort:** Data will be analyzed descriptively, including demographic and clinical characteristics of participants (i.e., age, sex, cancer or tumor-type, time since diagnosis, number of days in hospital during PRISM study). Eligible AYAs who decline to participate will be asked to provide a reason for declining the study and the above characteristics will be obtained from the medical record; such that we can compare participants and non-participants to determine biases in enrollment preferences.

**11.2 “Feasibility”** will be defined as: (1) at least 70% enrollment of approached and eligible patients; and (2) at least 70% completion of the 5 main PRISM sessions (not including “Coming

Together,” as we have done for prior feasibility determinations) among enrolled patients. “Acceptability” will be assessed qualitatively, as we have done in all prior pilot studies of PRISM’s development. Briefly, prior to each session (beginning with session #2), interventionists will solicit feedback regarding the usage and utility of the prior learned skill(s). Following the final session, we will solicit more detailed feedback regarding timing and value of the intervention and its content (see PRISM manual and Voicing My Choices session in appendices). Because the additional session involving early advance care planning is new for this study, we have designed additional pointed questions to gather user feedback about these exercises, including their perceived value, format preferences, timing, and if/how the session compares to the other skills (See Voicing My Choices appendix document). Finally, baseline and follow-up RPCA scores will be determined and these data will be entered into the secure database. For this pilot study, we will describe pre-and post-intervention scores and score changes for each instrument, with effect sizes calculated accordingly.

**11.3 Randomized Controlled Trial (RCT):** The primary statistical analyses will be intention-to-treat to avoid confounding by non-random participant attrition. Demographics, clinical characteristics, and items within the RPCA will all be summarized at each time-point using descriptive statistics: frequencies and proportions for categorical variables, means and standard deviations for continuous variables, or median and interquartile range if distribution is skewed. All analyses will be adjusted for patient age and site, as randomization is stratified by age and site, as well as baseline characteristics clearly imbalanced between groups. Additional baseline characteristics we consider as potential confounders include sex, race, and primary language spoken at home.

### 11.3.1 Sample Size Determination and Power

**11.3.1.1** Our focus for sample size estimation is *the primary outcome: AYA PedsQL generic core scores at 3-month observation*. Sample size is based on published data from the pediatric advanced cancer population, where baseline scores were normally distributed with mean 70.9 and standard deviation 17.2. Assuming 26% attrition, we will randomize 195 AYAs (98 per arm) to obtain an evaluable sample size of 144 AYA participants (72 per arm). This sample size achieves 80% power to detect an 8.1 point difference in the mean 3-month total PedsQL score (Table 6).

**11.3.1.2** Power calculations for select secondary AYA outcomes are listed in Table 6.

**11.3.1.3** Parent Reported Outcomes: Assuming >90% caregiver participation (as in our prior studies), we anticipate a minimum sample size of 128 caregivers (64 per arm). This caregiver sample size achieves  $\geq 80\%$  power to detect reasonable effects for parent outcomes, based on standard deviations and other parameters from our preliminary data and published literature (Table 7).

**Table 7. Detectable Differences in selected Mean Instrument Scores Between Groups Given 80% Power and 5% Type I Error Rate**

Aim	Sample (N)	Outcome (Instrument)	Sample Mean (SD)	Source	MCID*	DD (SD)
1	AYAs (144)	Quality of Life – General (PedSQL 4.0)	70.9 (17.2)	Published Data 	4.4	8.1 (17.2)
		AYA Quality of Life – Cancer (PedSQL 3.0 Cancer)	65.3 (16.3)	Phase II RCT	(not published)	7.7 (16.3)
		Anxiety (HADS-A)	5.9 (3.4)	Phase II RCT	1.3-1.8	1.6 (3.4)
		Depression (HADS-D)	5.2 (3.6)	Phase II RCT	1.5	1.7 (3.6)
		AYA Hope (Hope Scale)	Mean 50 (8.3)	Phase II RCT	(not published)	3.9 (8.3)
2	Parents (128)	Anxiety (GAD-7)	2.95 (3.4)	Published Data 	(not published)	1.7 (3.4)
		Depression (PHQ-8)	3.3 (3.7)	Published Data 	5	1.8 (3.7)
		HRQOL-physical (SF-36 PCS)	50.3 (6.9)	Published Data 	3-5	3.4 (6.9)
		HRQOL-mental (SF-36 MCS)	42.9 (11.9)	Published Data 	3-5	5.9 (11.9)

Legend: MCID: Minimal Clinically Important Difference (\*reported when published); DD: Detectable Difference in Mean

## 11.4 Randomization

**11.4.1** The randomization algorithm will be constructed by the study statistician using a permuted blocks scheme with varying block sizes; only the statistician will be aware of the block sizes until completion of the study. A statistician independent of the study will prepare the final randomization list, which will be administered by a clinical research associate independent of the study using the SCH/UW REDCap. Randomization will be stratified by age (patients ages 12-17 versus ages 18-25) and site.

## 11.5 Analysis Plan

**11.5.1 Overview.** The primary statistical analyses will be intention-to-treat to avoid confounding by non-random participant attrition. Demographics, clinical characteristics, and items within the RPCA will be summarized at each time-point using descriptive statistics: frequencies and proportions for categorical variables, means and standard deviations for continuous variables, or median and interquartile range if the distribution is markedly skewed. All analyses will be adjusted for site and patient age, as randomization is stratified by these 2 variables, as well as baseline characteristics clearly imbalanced between groups.

**11.5.2 Primary Outcome.** Our primary outcome is AYA reported HRQOL at 12 weeks. Because the amount of change depends strongly on the initial HRQOL at baseline we will control for baseline HRQOL as a covariate in the regression. Regression models will be used to estimate mean-level differences and 95% confidence

intervals comparing scores in the PRISM intervention to those in usual care. The mean total PedsQL generic core score will be the outcome, and the PRISM intervention the predictor, of interest. A generalization of the two-sample t-test based on a contrast of the regression model will examine if there is an increase in PedsQL scores from baseline for PRISM versus usual care at the primary time point of interest, 3 months following enrollment. The same analysis will be undertaken for the domain subscales of PedsQL (physical and psychosocial), the cancer-specific module, and secondary outcomes included in AYA surveys. Subgroup analyses will explore whether the effect of the intervention is modified by medical covariates, symptom distress, and/or concurrent parent distress. Response type (survey, interview, or parent proxy) will be included in sensitivity analyses and data reported separately if indicated. The rationale for these subgroup analyses is grounded in prior findings suggesting symptoms and parent wellbeing are associated with patient HRQOL.

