### 9.2 Randomization (RCT only)

**9.2.1** As a quality control measure, a randomization log will be maintained at SCH to track the participant ID, stratum, randomized assignment, and date of randomization. Patients will be randomized only after completion of baseline surveys and in a 1:1 ratio to receive usual, non-directive, supportive care without PRISM (“control” arm) or with PRISM (“experimental” arm). Randomization will be stratified by age (patients ages 12-17 versus ages 18-25) and site. Biostatisticians who will conduct data analysis will be blinded from the treatment group allocations.

**9.2.2** Throughout the screening period until allocation of the control or PRISM, participants will be assigned a screening number, according to the chronological order of screening. Once enrolled, the participant will be assigned a study ID.

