### 11.5.3 Secondary Outcomes

**11.5.3.1** The goal for parent outcomes is to evaluate the effect of the intervention on *parent psychological distress* and HRQOL. Mean total scores from each parent instrument at 12 weeks will be the secondary outcomes of interest. We will model distress and HRQOL separately and follow a similar approach to the analyses for continuous outcome measures in Aim 1. As sex and baseline patient HRQOL may be predictors of these outcomes, each will be included if imbalanced between arms.

**11.5.3.2** To compare patient and caregiver *activation*, we will measure patterns in multiple domains: AYA- and parent-reported Decision-Making Involvement Scores, AYA participation in goals of care conversations, and formal palliative care service utilization including documented referrals for hospice and charted decisions to limit resuscitative efforts. For all outcomes, results between trial groups will be compared using analysis of variance with trial group as the factor of interest. We will explore whether change in activation scores are correlated within families and/or modified by parent/child characteristics (sex, psychological distress scores, cancer/tumor-type, among others) using ordinal logistic regression models with cumulative logits, where change activation level is categorized as negative, null, or positive.

**11.5.3.3 Exploratory analyses** will evaluate prospective and longitudinal survey and clinical data beyond month 3 (primary endpoint) at months 6, 9, and 12 of the study. Comparisons between groups will still use an intention to treat approach as described above. Additionally, we will explore the relationship between biomedical variables and patient reported anxiety and depression through a combination of paired and unpaired t-tests, chi-squared (or Fisher's exact) tests, and linear and logistics regression. HRV will be measured in 24-hour increments using both time and frequency domain parameters as established by the international Cardiology task force

guidelines. Means and standard deviations will be compared to published normative data in adolescents.

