**11.5.3.4 Additional analyses** will include process evaluations that include: (a) intervention fidelity; (b) satisfaction queries; and (c) mediation analyses to evaluate relationships between PRISM, family activation, and outcomes. For example, the intervention effect on parent outcomes may be mediated by parent activation. If we find a positive intervention effect on parent psychological distress, we will explore activation mediation using the counterfactual framework with indirect mediation effects computed through G-estimation and incorporating confounders of the mediator-outcome association. Finally, we will conduct a planned interim analysis for data-safety monitoring purposes when half of AYA participants have reached the primary endpoint (see Human Subjects).

**11.5.3.5 Multiple comparisons.** Multiple comparisons are a concern since we are collecting multiple measures from both patients and caregivers and are interested in several hypotheses. We minimize this problem by specifying a limited number of main hypotheses for each aim. False Discovery Rate criterion will be used to correct for multiple testing in analyses that are not pre-specified. Likewise, in manuscripts and presentations, we will report the number of tests performed and interpret results within this context.

**11.5.3.6 Considerations regarding missing data.** Effective data collection at scheduled times will be monitored and attrition minimized as described below. While our goal will be to minimize missing data, data may still be missing due to patients/families skipping individual items, omissions in medical records, lack of follow-up, medical complications, or death. We will quantify the amount of missing data, evaluate the association of participant characteristics with missing data, and minimize bias and increase efficiency in the associations of interest by applying appropriate methods to account for missing data. For example, where missing at random (MAR) is a plausible assumption, we will use multiple imputation or inverse probability weighting, depending on the statistical model being considered. For missing not at random (MNAR), we will use sensitivity analyses. In all cases, we will assess the robustness of estimates due to assumptions.

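### Parent models admit two named possible predictors only if they happen to be imbalanced, and other covariates enter on an undefined imbalance criterion, which can give up a little precision

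*Combined protocol and SAP*

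**What the plan says.** Part of the covariate set is fixed. Sections 11.3 and 11.5.1 adjust all analyses for patient age and site, the stratification factors. For the primary outcome, 11.5.2 adds the baseline score: "we will control for baseline HRQOL as a covariate in the regression".

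Beyond that, entry depends on the observed baseline data. Section 11.5.1 adjusts for site and age, "as randomization is stratified by these 2 variables, as well as baseline characteristics clearly imbalanced between groups", and 11.3 says the same. Section 11.3 goes part of the way to naming candidates: "Additional baseline characteristics we consider as potential confounders include sex, race, and primary language spoken at home". The list is open-ended, and neither section gives a test, cut-off, decision-maker or date for settling the model.

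For parent outcomes, 11.5.3.1 says the models will "follow a similar approach to the analyses for continuous outcome measures in Aim 1". It then gives two further candidates and an entry rule: "As sex and baseline patient HRQOL may be predictors of these outcomes", "each will be included if imbalanced between arms". It does not say whether the sex is the parent's or the patient's.

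Two safeguards bear on this. Section 9.2.1 states: "Biostatisticians who will conduct data analysis will be blinded from the treatment group allocations". Section 11.5.3.5 states: "False Discovery Rate criterion will be used to correct for multiple testing in analyses that are not pre-specified".

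**The concern.** In a randomized trial any baseline difference between arms is a chance event. The case for putting a covariate in the model is that it predicts the outcome, because it then removes residual variance whether or not the arms differ on it. The plan uses that reasoning for the primary outcome, where baseline HRQOL is fixed because change depends on it. It departs from it for parent outcomes, where two variables are put forward as possible predictors and then left out unless they happen to be imbalanced.

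What is at stake is mainly precision in the secondary parent outcomes (GAD-7, PHQ-8, SF-36). A lesser matter is that the models cannot be fully programmed from the text, since imbalance is undefined and the sex variable is ambiguous.

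**Working it through.** **Inputs from the documents (11.3.1, Table 7).** Parents: 64 per arm; PHQ-8 difference 1.8, SD 3.7; GAD-7 difference 1.7, SD 3.4. AYAs: 72 per arm; PedsQL difference 8.1, SD 17.2. Type I error 5%, taken as two-sided.

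**Assumptions, because the documents give no values.** The parent's own baseline score is in the model and correlates 0.5 with the outcome. The two extra covariates (one binary, one continuous) are independent, each with partial correlation ρ from 0 to 0.3. Triggers tried: baseline p<0.05, p<0.10, standardized mean difference (SMD) above 0.2, and SMD above 0.1.

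**Step 1: the plan's own figures.** Noncentrality = difference / (SD × √(2/n)), unadjusted t-test.
- PedsQL: 8.1 / (17.2 × √(2/72)) = 8.1 / 2.867 = 2.83, power 80.1%.
- GAD-7: 1.7 / (3.4 × √(2/64)) = 1.7 / 0.601 = 2.83, power 80.1%.
- PHQ-8: 1.8 / (3.7 × √(2/64)) = 1.8 / 0.654 = 2.75, power 78.0%. The unrounded detectable difference is about 1.83, so this is rounding in the table.

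The stated 80% is reproduced. It uses unadjusted SDs and takes no credit for covariates.

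**Step 2: how often a trigger admits a covariate.** A p<0.05 trigger admits a given covariate in 5% of trials, and leaves both out in 0.95² = 90%. With 64 per arm the chance SMD has standard deviation √(2/64) = 0.177, so SMD above 0.1 occurs with probability 2 × {1 − Φ(0.1/0.177)} = 57%. A significance-type trigger therefore forgoes nearly all of any gain; the loosest trigger keeps a good part of it.

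**Step 3: standard error if both are always included.** SE ≈ SD × √(1 − 0.5²) × √(1 − 2ρ²) × √(2/64) = 3.7 × 0.866 × 0.1768 × √(1 − 2ρ²) = 0.566 × √(1 − 2ρ²).
- ρ = 0.2: 0.543 (simulated mean 0.549, slightly larger because covariates cost degrees of freedom).
- ρ = 0.3: 0.513 (simulated mean 0.518).

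Under the imbalance rule the simulated mean SE is 0.568 (p<0.05) to 0.559 (SMD above 0.1) at ρ = 0.2, and 0.566 to 0.543 at ρ = 0.3. Always including narrows the interval by 2-3% and 5-8% respectively.

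**Step 4: PHQ-8 power by simulation, p<0.05 trigger.** Where two values appear, they come from separate runs of 6,000 and 40,000 trials; single values come from the 6,000-trial run.

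| Partial ρ | Imbalance rule | Always included | Given up (points) |
|---|---|---|---|
| 0 | 87.1% | 86.8% | −0.3 |
| 0.1 | 88.1% | 88.4% | 0.3 |
| 0.2 | 87.6%, 88.2% | 89.1%, 90.0% | 1.5, 1.8 |
| 0.3 | 89.0%, 88.9% | 92.9%, 93.2% | 3.9, 4.3 |

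With SMD above 0.1 the loss falls to 90.0 − 89.3 = 0.7 points at ρ = 0.2 and 93.2 − 91.8 = 1.4 at ρ = 0.3.

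**Step 5: sensitivity, p<0.05 trigger.**
- Only one covariate prognostic: 88.9 − 87.9 = 1.0 point at ρ = 0.2; 90.9 − 88.4 = 2.5 at 0.3.
- Baseline correlation 0.3: 83.7 − 81.4 = 2.3 and 87.7 − 82.1 = 5.6.
- Baseline correlation 0.7: 97.6 − 96.9 = 0.7 and 98.7 − 97.1 = 1.6.
- GAD-7, baseline correlation 0.5: 91.6 − 90.0 = 1.6 and 94.2 − 90.3 = 3.9.

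**Step 6: primary outcome.** With baseline PedsQL in the model (r = 0.5) and one extra covariate, across all triggers, power is 90.0-90.6% against 90.9% at ρ = 0.2, and 90.1-91.6% against 92.4% at ρ = 0.3: a difference of 0.3 to 2.3 points. This is illustrative, since 11.3 names three candidates and does not call any of them a predictor of HRQOL.

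**Step 7: type I error.** Applied mechanically at ρ = 0.2 or 0.3, the rule rejects a true null in 4.1-4.7% of parent trials and 4.6-4.9% of primary trials, against 5.0% for the always-included parent model.

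**The case against.** The strongest reply is that nothing the plan promises fails. With the parent's own baseline score in the model at a correlation of 0.3 or more, every simulated PHQ-8 power under the disputed rule exceeds 80%, and the sample size never relied on covariates. That stands: what is given up is an efficiency gain the plan did not claim.

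Second, 11.5.3.1 says only that the two variables may be predictors. Once the parent's own baseline score is in the model, it may already carry much of the association, leaving small partial correlations. That also stands, and is why the range starts at zero, where always including them costs a fraction of a point.

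Third, 11.3 names sex, race and home language, and 11.5.3.1 names two candidates, so the pool is not wholly open. This is fair. What is missing is the entry criterion, a closed list and the identity of the sex variable.

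A reader might go further and infer that the loose wording inflates type I error. Taking the smaller p-value of the models with and without the covariates would give about 6-7% on a single test under the assumed correlations. The plan does not permit that: selection by outcome p-value is not selection by baseline imbalance, and analysts are blinded to allocation. The false discovery rate provision addresses analyses that are not pre-specified; it neither defines the covariate rule nor is needed to rebut this reading.

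**Conclusion.** The point holds as a minor one. The parent rule makes two possible predictors depend on chance imbalance, and always including them is the better method at almost no cost. For PHQ-8 with a p<0.05 trigger and baseline correlation 0.5, the loss is none to negligible at partial correlations of 0 to 0.1, 1 to 2 points at 0.2 and about 4 points at 0.3. It is smaller with looser triggers or a stronger baseline correlation, and somewhat larger with a weaker one. All correlations and triggers are assumptions. The undefined threshold and the ambiguous sex variable are gaps in detail that the same edit closes.

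The documents do not support reading this as a power shortfall: the 80% figures reproduce, and the 78.0% for PHQ-8 reflects a rounded detectable difference. Nor do they support a claim of inflated type I error, which stays at or slightly below 5% if the rule is followed mechanically. The primary analysis is little affected, because age, site and baseline HRQOL are already fixed.

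**What to change.** In 11.5.3.1, specify the parent models as treatment, the parent's own baseline score, age stratum, site, baseline AYA PedsQL and sex, always included, and state whether sex is the parent's or the patient's.

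In 11.3 and 11.5.1, replace the imbalance clause with a covariate list fixed before outcome data by arm are seen. For the primary model: treatment, baseline PedsQL, age stratum, site and any further covariate named in advance. Models that add characteristics found to be imbalanced can stay as labelled sensitivity analyses.

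The cost is wording and one or two degrees of freedom among 128 caregivers, with a negligible loss of precision if the covariates prove not prognostic. No new data are needed: AYA baseline surveys precede randomization (9.2.1), parents are surveyed at the same time points as AYAs (4.1), and sex is a standard survey item (9.6).
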